Conjugated estrogens/bazedoxifene	0.45 milligrams/20 milligrams/day	Oral tablet						

	Drug	Route of Administration
	Conjugated estrogens/bazedoxifene	Oral
Regimen:		
Once determined eligible and physically well, participants with perimenopausal depression will receive a tissue selective estrogen complex (TSEC) (conjugated estrogens/bazedoxifene, 0.45mg/20mg) for 3 weeks. Prior to beginning medication, women will have a basic lab panel and serum pregnancy test, pelvic exam, breast exam, and PAP smear. Participants who can provide record of a pelvic exam and breast exam within the past year and normal pap results within the past three years will be permitted to decline the GYN exam. Women will be seen in the clinic each week during TSEC administration to assess blood levels of estradiol and mood symptoms.		
Duration of administration	3 weeks	
Reference population	Perimenopausal women, non-depressed	
Statistical Methodology:	We will test our H1 hypothesis using a paired t-test of MASQ Anhedonia scores at visit 1 (pre-treatment) and visit 6 (post-treatment). We will test our H2 hypothesis using a paired t-test to compare activity in 3 regions of interest (ROIs)—caudate, putamen, and nucleus accumbens—at the pretreatment and posttreatment scans.	

1 Introduction

This document is a protocol for a human research study. This study is to be conducted according to US and international standards of Good Clinical Practice (FDA Title 21 part 312 and International Conference on Harmonization guidelines), applicable government regulations and Institutional research policies and procedures.

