3.1 General Design

Overview. This is an observational, single-center study using tissue-selective estrogen complex (TSEC) to examine the role of frontostriatal hypoactivity in the pathophysiology of perimenopausal MDD. This study will include 6 study visits that will take place over the course of approximately 6 weeks. Out of those 6 visits, 2 of them will require subjects to come to UNC's campus for their MRI visits at BRIC, while the rest of the appointments will be done virtually through HIPAA compliant Zoom, Webex, or phone when zoom is not available. Five visits will require brief in-person contact for phlebotomy, these very brief points of contact will be performed outside the subject's home when possible (i.e. backyard, back porch, or screened porch). In the context of COVID-19, all participants and staff will complete the appropriate screening as recommended by UNC and BRIC policy prior to any in-person contact. During in person visits participants and the study team will be required to wear masks at all times and maintain 6 feet distance when possible to minimize the possibility of COVID-19 transmission. Perimenopausal MDD women will receive Duavee, a TSEC, for 3 weeks. FMRI sessions will occur at baseline and at the end of the third week of medication administration. The procedures that will take place are outlined in **Table 1** and detailed below.

Table 1. Study Procedures and Timeline

Study Visits	1	2	3	4	5	6
Maximum duration of in-person visit (hours)		1	2	0.15	0.15	2
Consent	X					
OBGYN Exam		X				
fMRI			X			X
PRT			X			X
Venipuncture		X	X	X	X	X
SCID	X					
SNAP	X		X	X	X	X
HAM-D	X		X	X	X	X
IDAS	X		X	X	X	X
GCS	X		X	X	X	X
PSQI			X			X
HHQ						X
THQ						X
Duavee Rx Provided			X	X	X	
Payment	\$100	\$30	\$150	\$35	\$35	\$150

Participants. Participants will include healthy, unmedicated perimenopausal women ages 44-55 with (n=20) current major depression.

Hormone Administration.

Prior to beginning medication, women will have a basic lab panel and serum pregnancy test, pelvic exam, breast exam, and PAP smear. Participants who can provide record of a pelvic exam and breast exam within the past year and normal pap results within the past three years will be permitted to decline the GYN exam. Women will be seen in the clinic each week during medication administration to assess blood levels of estradiol and mood symptoms.

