5.7 Packaging

The UNC Investigational Drug Service will receive the active drug from their Pharmacy storeroom. All the Duavee tablets will be provided to participants at study visit 3, in its original blister packaging. Duavee tablets are to be taken once daily. The remaining tablets will be returned to the study team at the conclusion of each subject's participation in the study, and returned to IDS for appropriate disposal.

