5.9.4 Return or Destruction of Study Drug

At the completion of the study, there will be a final reconciliation of drug shipped, drug consumed, and drug remaining. This reconciliation will be logged on the drug reconciliation form, signed and dated. Any discrepancies noted will be investigated, resolved, and documented prior to return or destruction of unused study drug. Drug destroyed on site will be documented in the study files.

6 Study Procedures

The flowchart outlining the procedures at each study visit it attached.

OBGYN Exam

Prior to beginning medication, women will have a basic lab panel and serum pregnancy test, pelvic exam, breast exam, and PAP smear. Participants who can provide record of a pelvic exam and breast exam within the past year and normal pap results within the past three years will be permitted to decline the GYN exam. Results of the exam will be added to the participants' UNC Hospital medical record.

Venipuncture

Participants will undergo venipuncture at 5 study visits. Initial blood tests will include BUN, creatinine, ALT, AST, potassium, chloride, calcium, alkaline phosphatase, and a CBCD to rule out exclusionary health problems. Lab results will be added to participants' medical records. Subsequent venipuncture will be for the purpose of assaying estradiol levels to ensure participant compliance. During the context of COVID-19 venipuncture will be carried out by fully vaccinated study team members in private outdoor settings when possible, such as the subject's backyard.

Drug Administration

Participants will receive their entire supply of Duavee at study visit 3.

Clinical Assessments

The Structured Clinical Interview for DSM-IV-TR Axis-I Disorders (SCID)⁵⁸ and the Schedule for The SCID1 will be administered at baseline to determine study eligibility. The following standard measures will be administered at baseline, both fMRI sessions, and weekly clinic visits:

- The Positive and Negative Affect Schedule⁵⁹ is a 20-item questionnaire that measures both positive affect (PA) and negative affect (NA) and is sensitive to subtle changes in affect over time.

- The Hamilton Rating Scale for Depression (HRSD)⁶⁰ is a 21-item researcher-rated standardized scale that assesses depressive symptoms and is widely used as a measure of symptom change over time.

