7.2 Statistical Methods

Aim 1: Determine the extent to which TSEC reduces anhedonia and other depressive symptoms in PM-MDD. Anhedonia and other depressive symptoms will be assessed at baseline and following 3 weeks of TSEC administration. Null hypothesis (H0): TSEC has no salutary effect on depression. Alternative hypothesis (H1): TSEC reduces depression as evidenced by 1) a statistically significant decrease in average MASQ Anhedonia scale score following 3 weeks of treatment, and 2) a clinically significant increase of 1 SD in MASQ Anhedonia scale score. We will test this hypothesis using a paired t-test of MASQ Anhedonia scores at visit 1 (pre-treatment) and visit 6 (post-treatment).

Aim 2 (Exploratory): Quantify the effect of TSEC on the neural reward system in PM-MDD. We will use fMRI at baseline and following TSEC treatment in PM-MDD to probe frontostriatal reward circuitry. We also will compare the effects of TSEC and ERT in PM-MDD. Null hypothesis (H0): TSEC has no meaningful effect on activity of the neural reward circuit in response to rewards. Alternative hypothesis (H1): TSEC reduces increases neural responsiveness to reward in the frontostriatal reward circuitry as evidenced by increased activation of the caudate, putamen, and nucleus accumbens in PM-MDD in response to reward following TSEC administration (compared with baseline). We will test this hypothesis using a paired t-test to compare activity in 3 regions of interest (ROIs)—caudate, putamen, and nucleus accumbens—at the pretreatment and posttreatment scans.

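### The Aim 1 paired t-test starts at visit 1, but Duavee is first supplied at visit 3, so about half of the tested interval is untreated

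*Combined protocol and SAP*

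**What the plan says.** The Aim 1 hypothesis in section 7.2 is about "a statistically significant decrease in average MASQ Anhedonia scale score following 3 weeks of treatment", with a further 1 SD criterion. The test is stated there as: "We will test this hypothesis using a paired t-test of MASQ Anhedonia scores at visit 1 (pre-treatment) and visit 6 (post-treatment"). The same two visits are named in the Study Summary, section 2, section 7.2 and Appendix A (statistical analysis strategy).

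The schedule is as follows.

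- **Visit 1:** consent, SCID and initial evaluation (Table 1; section 12.3).
- **Visit 2:** physical exam and baseline labs (section 12.3).
- **Visit 3:** first scan and first supply of drug. Section 5.7: "All the Duavee tablets will be provided to participants at study visit 3". Section 6, Drug Administration: "Participants will receive their entire supply of Duavee at study visit 3". Both visit tables also mark Duavee at visits 4 and 5, but nothing in the documents supplies it before visit 3.
- **Length:** section 3.1 says "This study will include 6 study visits that will take place over the course of approximately 6 weeks" and "Perimenopausal MDD women will receive Duavee, a TSEC, for 3 weeks".
- **Scans:** section 3.1 says "FMRI sessions will occur at baseline and at the end of the third week of medication administration". Table 1 puts these at visits 3 and 6.

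The Clinical Assessments lists in section 3.1, section 6 and Appendix A include the MASQ-AD among measures given at baseline, both scan sessions and the weekly visits. Neither visit table has a MASQ-AD row. Section 1.1 accepts the absence of a placebo arm.

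**The concern.** The hypothesis is about 3 weeks of treatment, but the test covers the whole study. Visit 1 does precede treatment, but its score is not the last one planned before the first tablet. Between it and visit 3 lie the exam, the labs and an unspecified stretch of time; no visit 1-to-3 window is given, so the untreated time may also differ between women.

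In a single-arm study nothing separates change in that stretch from change on drug. A spontaneous fall in anhedonia before visit 3 would flatter the TSEC, and a worsening would hide an effect. The reasons section 1.1 gives for having no placebo arm, scanning cost and sample size, do not bear on which visit serves as baseline.

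The two aims also start at different points. Aim 2 compares the visit 3 and visit 6 scans, whereas Aim 1 compares visits 1 and 6. The central hypothesis in section 2 links the antidepressant effect to the change in reward activity, yet the first would be measured over about 6 weeks and the second over 3.

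**Working it through.** **1. The plan's own figure.** Section 7.1 gives 80% power for an effect of 0.7 in 20 women. Alpha is not stated; I assume 5% two-sided and read 0.7 as the mean change divided by the SD of the change. For a paired t-test, df = 19, critical t = 2.093 and noncentrality = 0.7 × √20 = 3.13. Power is 84.4%. The smallest n reaching 80% is 19 (82.3%; n = 18 gives 79.9%). The sample size reproduces and is not in question.

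**2. Untreated share of the tested interval.** Share = (span of visits 1 to 6 − 3 weeks of treatment) / span. At the stated 6 weeks this is (6 − 3)/6 = 50%. Because the span is approximate:

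| Span (weeks) | Untreated share |
|---|---|
| 4 | 25% |
| 5 | 40% |
| 6 | 50% |
| 7 | 57% |

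**3. What untreated change could do (illustration only).** The documents give no visit 1-to-3 change, no MASQ SD and no pre-post correlation. Assumptions: score SD = 1, correlation r between 0.3 and 0.7, SD of change = √(2(1 − r)), that is 1.183, 1.000 and 0.775 for r = 0.3, 0.5 and 0.7.

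*Inert drug, untreated fall f before visit 3.* P(significant decrease) = P(T > 2.093), where T is noncentral t with 19 df and noncentrality f/√(2(1 − r)) × √20.

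| f (SD) | r = 0.3 | r = 0.5 | r = 0.7 |
|---|---|---|---|
| 0 | 2.5% | 2.5% | 2.5% |
| 0.05 | 3.8% | 4.0% | 4.6% |
| 0.1 | 5.5% | 6.2% | 7.9% |
| 0.2 | 10.7% | 13.4% | 19.4% |
| 0.3 | 18.9% | 24.7% | 37.6% |

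*Worsening w before visit 3, drug effect 0.7.* The paired effect becomes 0.7 − w/√(2(1 − r)).

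| w (SD) | r = 0.3 | r = 0.5 | r = 0.7 |
|---|---|---|---|
| 0 | 84.4% | 84.4% | 84.4% |
| 0.1 | 74.3% | 72.1% | 67.8% |
| 0.2 | 61.5% | 56.5% | 46.6% |

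**4. Both parts of H1 together.** The 1 SD criterion is worded as an increase, and the text does not say whether it applies to the group or to each woman. Read as a group-mean fall of at least one baseline SD together with a significant t-test, 200,000 simulated trials per setting with an inert drug give:

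| f (SD) | r = 0.3 | r = 0.5 | r = 0.7 |
|---|---|---|---|
| 0.1 | 0.21% | 0.06% | 0.01% |
| 0.2 | 0.52% | 0.20% | 0.03% |
| 0.3 | 1.24% | 0.59% | 0.15% |

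**5. What a visit 3 baseline changes.** Suppose scores fall steadily by 0.1 SD per 3 weeks regardless of treatment. From visit 1 the total is 0.2 SD and the t-test rate is 11-19%. From visit 3 it is 0.1 SD and 5-8%. This uses the same range of r for both intervals, which is itself an assumption.

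**The case against.** The case for leaving the plan alone has five parts.

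- **The span is approximate.** About half comes from two rounded durations. This stands, and the range is 25% to 57%. Even at the low end a quarter of the interval is untreated.
- **No drift is documented.** Entry is by SCID diagnosis with no MASQ cut-off, so the documents give no selection on the tested score that would make a fall expected. This stands too: the error rates and power losses are illustrations. The mismatch between hypothesis and test does not depend on them.
- **Drift seldom satisfies the whole of H1.** On the group-mean reading of the 1 SD criterion, false success is about 1.2% at most in these settings. The main harm is therefore bias in the estimate rather than false claims of full success, though that reading is not settled by the text.
- **The larger weakness remains.** This is an open, single-arm pilot, and expectancy and natural course during the treated weeks are untouched by a visit 3 baseline. That is right, and the fix is partial. But the pilot is meant to inform a larger placebo-controlled trial, so an estimate over the wrong interval would carry forward.
- **A visit 3 MASQ-AD is not certain to be collected.** It rests on a general sentence heading a list. The hormone and trauma history questionnaires are in the same list, yet the tables place them at visit 6 only. If staff worked from the tables, the visit 3 score would be new data collection and could not be recovered for women already past that visit. This needs to be confirmed.

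No part of the documents justifies choosing visit 1 over visit 3 or adjusts for change between them.

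**Conclusion.** The concern holds. As written, the Aim 1 test measures change over about 6 weeks, of which about 3 are untreated, while H1 concerns 3 weeks of treatment. With no control arm, any change before the first tablet goes straight into the estimate. That follows from the schedule alone and needs no assumption beyond the stated durations.

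How much it matters in practice cannot be read from the documents. Under the assumptions shown, an untreated shift of 0.1 to 0.2 SD raises the chance of a significant decrease with an inert drug to 5-19%, or lowers power from 84% to 47-74%, depending on its direction. It should be fixed: it affects the only test of the only aim not labelled exploratory, but it does not invalidate the trial or alter the sample size.

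**What to change.** - In the Study Summary, sections 2 and 7.2 and Appendix A, name the visit 3 MASQ-AD, completed before the first tablet, as the pre-treatment score for Aim 1.
- Add a MASQ-AD row (visits 1, 3, 4, 5 and 6) to Table 1 and to the Appendix A visit table, so that both match the text. Confirm whether the form has in fact been given at visit 3.
- Report the visit 1-to-3 change, with its length in days, as an untreated run-in beside the visit 3-to-6 change.
- State that uncontrolled change from visit 3 to visit 6 remains in the estimate.

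The cost is wording in four places and one row in each of two tables. No visit is added. If staff have followed the tables rather than the text, it adds one 22-item self-report form at visit 3, and women already past that visit will lack the score. The estimate may turn out less favourable than one taken from visit 1.

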7.3 Subject Population(s) for Analysis

Given that we are interested in understanding the effect of TSECs on brain function, only data from protocol-compliant participants will be subjected to the study analysis.

8 Safety and Adverse Events

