4.4 Early Withdrawal of Subjects

4.4.1 When and How to Withdraw Subjects

Participants with significant clinical or laboratory abnormalities will be discontinued from the study prior to estrogen administration.

Adverse mood symptoms will be monitored by administering the Hamilton Rating Scale for Depression (HRSD) at each study visit. If suicidal thoughts or severe mood symptoms are **observed at any period in the protocol, then the HRSD will be administered on consecutive days for three days. Anyone scoring > 20 on the HRSD or expressing concerns about their ability to continue in the study, will be considered to have severe mood symptoms and be discontinued from the protocol.** In the event of the occurrence of severe mood symptoms, the protocol will be terminated. Should this step prove to be unsuccessful, conventional medication will be prescribed as needed. Further, although we do not anticipate severe adverse reactions, we have arranged for inpatient hospital admission in the Psychiatry Department if symptoms are otherwise unmanageable.

Any patient experiencing clinically significant side effects such as nausea, hypertension, vomiting or extreme fluid retention from the medication will have the dose titrated to achieve relief of the symptoms. If adequate relief cannot be achieved in this manner, drug treatment will be discontinued.

The determination of when and how to withdrawal subjects will be overseen by the study's principal investigator, co-investigators, and research coordinators and will be reported to the UNC Biomedical IRB.

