4.4.2 Data Collection and Follow-up for Withdrawn Subjects

Participants who elect to discontinue the hormone protocol or are discontinued for safety reasons will be asked to continue to complete self-report ratings through the end of the proposed study period. However, fMRIs will not be done if participants discontinue the hormone protocol.

5 Study Drug

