5.5 Subject Compliance Monitoring

We will monitor participants' compliance with the drug regimen by assaying blood levels of medication collected at weekly study visits. The drug protocol will be reviewed at each study session, and participants who are significantly non-compliant with the study treatment regimen will be discontinued from the study.

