8.3.5 Sponsor reporting: *Notifying participating investigators*

N/A

8.4 *Unblinding Procedures*

N/A

8.5 *Stopping Rules*

The protocol only includes rules for discontinuing individual participant, but not rules for stopping the entire study:

Adverse mood symptoms will be monitored by administering the Hamilton Rating Scale for Depression (HRSD) at each study visit. If suicidal thoughts or severe mood symptoms are observed at any period in the protocol, then the HRSD will be administered on consecutive days for three days. Anyone scoring > 20 on the HRSD or expressing concerns about their ability to continue in the study, will be considered to have severe mood symptoms and be discontinued from the protocol. In the event of the occurrence of severe mood symptoms, the protocol will be terminated. Should this step prove to be unsuccessful, conventional medication will be prescribed as needed. Further, although we do not anticipate severe adverse reactions, we have arranged for inpatient hospital admission in the Psychiatry Department if symptoms are otherwise unmanageable.

8.6 *Medical Monitoring*

The principal investigator will oversee the safety of the study at her site. This safety monitoring will include careful assessment and appropriate reporting of adverse events as noted above, as well as the construction

and implementation of a site data and safety-monitoring plan. Medical monitoring will include a regular assessment of the number and type of serious adverse events.

The Principal Investigator's responsibilities are to:

- review the research protocol, informed consent documents, and plans for data safety and monitoring;
- evaluate the progress of the trial, including periodic assessments of data quality and timeliness, participant recruitment, accrual and retention, participant risk versus benefit, performance of the trial site, and other factors that can affect study outcome;
- consider factors external to the study when relevant information becomes available, such as scientific or therapeutic developments that may have an impact on the safety of the participants or the ethics of the trial;
- protect the safety of the study participants;
- report on the safety and progress of the trial;
- make recommendations to the UNC-CH IRB, and the PI, concerning continuation, termination, or other modifications of the trial based on the observed beneficial or adverse effects of the treatment under study;

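### Section 7.3 limits the uncontrolled Aim 1 mood test to an undefined protocol-compliant set chosen for a brain-function reason, which most naturally drops women stopped for worse mood and leaves their requested ratings unused

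*Combined protocol and SAP*

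**What the plan says.** Section 7.3 is a single sentence. Because the interest lies in how TSECs affect brain function, "only data from protocol-compliant participants will be subjected to the study analysis". It gives no definition, no separate set for Aim 1 and no sensitivity analysis. Section 7.2 tests Aim 1 by a paired t-test of the MASQ Anhedonia score, visit 1 against visit 6, with no rule for missing scores. Only Aim 2, the imaging aim, is labelled exploratory.

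The nearest text to a definition is section 5.5, which monitors compliance by blood levels and adds that "participants who are significantly non-compliant with the study treatment regimen will be discontinued from the study". It sets no threshold. Section 6 likewise ties the estradiol assays to compliance.

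Withdrawal for mood is described in sections 4.4.1 and 8.5 and in Appendix A, III.C. The rule covers "Anyone scoring > 20 on the HRSD or expressing concerns about their ability to continue in the study". As section 8.5 puts the consequence, such a woman "will be considered to have severe mood symptoms and be discontinued from the protocol". Ahead of that step, once suicidal thoughts or severe symptoms have been noticed, the same sections call for repeat ratings: "then the HRSD will be administered on consecutive days for three days".

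Section 4.4.2 says that women who stop by choice or for safety "will be asked to continue to complete self-report ratings through the end of the proposed study period", but "fMRIs will not be done if participants discontinue the hormone protocol". Sections 3.1 and 6 list MASQ-AD among the measures for baseline, both scans and the weekly visits. They name only the SCID and HAM-D as researcher administered, so MASQ-AD is self-report. Neither Table 1 nor the Appendix A visit table has a MASQ-AD row.

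**The concern.** The reason given in 7.3 belongs to the imaging aim, but the restriction also governs the mood aim. For a woman stopped before visit 6, section 4.4.2 already rules out the second scan, so 7.3 has no scan pair to remove. What it can remove is her later MASQ-AD.

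If women discontinued for high HRSD are not protocol-compliant, inclusion in the Aim 1 test depends on mood during treatment, which is closely related to the outcome. Removing women whose mood worsens on treatment moves the mean change toward benefit. There is no control arm in which the same selection would operate. Because the set is undefined in an open-label study of 20 women, it could also be settled after scores are known. Section 1.1 intends the result as pilot data for a placebo-controlled trial, so any inflation would carry into the planning of that trial.

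**Working it through.** **The plan's own figure.** Section 7.1 gives 80% power for an effect of 0.7 in 20 women. Alpha is not stated; 5% two-sided is assumed. For a paired t-test, power comes from the noncentral t distribution with n − 1 degrees of freedom and noncentrality d√n. At n = 20, 0.7 × √20 = 3.13 and power is 84.4%; the smallest n giving 80% is 19. The sample size therefore reproduces.

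**Power after exclusions.** At d = 0.7, power is 79.9% with 18 women and 71.3% with 15. At the d = 1.15 that 7.1 cites from the estradiol study, it is 98.5% with 15 and 95.1% with 12. Power is a lesser concern if that effect holds.

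**Size of the selection effect.** The documents give no HRSD mean, SD, correlation or withdrawal rate, so every input here is assumed:

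- no true mean change, and 20 women starting treatment;
- HRSD SD 5, with entry mean 14, 17 or 20;
- correlation 0.7 between visits, and 0.6 between HRSD and MASQ-AD;
- individual linear trends with SD 0.5 or 0.8 of the visit SD by visit 6 (2.5 or 4 HRSD points).

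The reading taken as closest to the text is this: a visit reading above 20, followed by three further readings all above 20, prevents treatment if it occurs at visit 1 or 3, and removes the woman if it occurs at visit 4 or 5. Monte Carlo results for the women kept:

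| Trend SD | Entry mean | Starters removed | Spurious improvement (SD) | False significant decrease (nominal 2.5%) |
|---|---|---|---|---|
| 0.5 | 14 | 2.5% | 0.005 | 2.6% |
| 0.5 | 17 | 6.6% | 0.011 | 2.8% |
| 0.5 | 20 | 13.2% | 0.021 | 3.1% |
| 0.8 | 14 | 3.8% | 0.020 | 2.9% |
| 0.8 | 17 | 8.8% | 0.042 | 3.6% |
| 0.8 | 20 | 16.1% | 0.073 | 4.4% |

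- The last row needs about 35% of women to be removed before dosing.
- Varying the HRSD–MASQ correlation from 0.4 to 0.8 gives 0.00 to 0.10 SD and 2.6 to 5.5%.
- Without individual trends there is no spurious benefit (0.00 to 0.01 SD worsening).
- Removal on single readings at visits 4 and 5 only reaches 0.18 SD and 6%, but that setting removes about 62% of starters, or 0.62 × 20 ≈ 12 women.
- Removal on single readings with the rule also applied before dosing gives 0.01 SD worsening to 0.06 SD improvement.

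**The alternative set.** Using the observed visit 6 score of every starter in the closest case gives 0.00 to 0.015 SD worsening and 2.2 to 2.4%.

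Section 4.4.1 foresees conventional medication after withdrawal, which could itself improve visit 6 scores. The gain in every withdrawn woman that would make the all-starter result as biased as the compliant set is (kept shift − all-starter shift) / share removed. For the last row, taking 0.015 SD worsening for all starters, this is (0.073 + 0.015) / 0.161 ≈ 0.55 SD. Across settings it is 0.28 to 0.60 SD. Using the last score before such treatment instead gives results from 0.02 SD worsening to 0.00.

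**The case against.** The strongest objection is that a woman stopped under 4.4.1 has followed the protocol, and that the only compliance text concerns the drug regimen. On that reading she stays in, no mood-linked exclusion arises, and only a missing definition remains. This stands as a possible reading. A reader might infer that 7.3 expressly excludes women with HRSD above 20; it does not say so. Exclusion is the more natural reading because these women are discontinued from the protocol itself, but 7.3 leaves the matter open.

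Second, the effect is small. The largest closest-case shift is about a tenth of the 0.7 used for sizing, and Aim 1 also asks for a 1 SD change. This stands too. A reader might infer serious inflation from the 0.18 SD setting, or from a model that deletes the women with the worst HRSD change. The first removes an implausible share of women. The second does not match a rule based on a score level.

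Third, the closest reading is a modelling choice. The text does not say that all three repeat readings must exceed 20, the stated trigger is observed symptoms and not a visit score, and withdrawal for concern about continuing or for suicidal ideation is not modelled. This is correct and limits the precision of any figure.

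Fourth, the central hypothesis in section 2 links antidepressant effect to reward activity, which gives some reason for a common set with both mood and scan data. That supports such a set as an additional analysis, but not as the only Aim 1 analysis.

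Finally, a reader might infer that the design could never reveal the selection. That goes too far. Section 4.4.2 requests the ratings that would show it, and the annual report in Appendix A covers reasons for dropout. The gap is that 7.3 does not put those ratings to use.

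**Conclusion.** The point holds, with medium confidence, and should be fixed. Section 7.3 applies one undefined set, with a reason that concerns imaging, to the uncontrolled mood test. On the more natural reading this ties inclusion to mood during treatment and discards ratings that the protocol requests.

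The consequence is small: about 0.00 to 0.07 SD toward benefit and 2.6 to 4.4% false improvement against 2.5% nominal. It rests on exclusion being the intended reading, on the assumed HRSD distribution and correlations, and on women differing in their trends. The upper end needs about 35% of women to be removed before dosing. The case for change is that the set is unsettled and the remedy uses data already planned, not that the bias is large. The withdrawal rule itself is not questioned.

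**What to change.** Rewrite 7.3 along these lines:

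- The Aim 1 primary set is every woman who took at least one tablet and has a visit 6 MASQ-AD, collected under 4.4.2 whether or not she stopped Duavee. The paired t-test of 7.2 is unchanged.
- The start of any other antidepressant treatment is recorded. A sensitivity analysis replaces scores obtained after it by the last MASQ-AD before it.
- Missing visit 6 scores and all exclusions are reported by reason.
- The protocol-compliant set is kept for the fMRI aim and as an Aim 1 sensitivity analysis. The sponsor fixes its criterion before analysis, from the blood levels (5.5) and tablet reconciliation (5.9.3) already collected, and states whether women stopped under 4.4.1 belong to it.

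Add a MASQ-AD row to Table 1 and to the Appendix A visit table so that they match the assessment lists in sections 3.1 and 6.

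The cost is protocol wording, two table rows and one recorded date, with no new visits or scans. Withdrawn women are only asked to continue, so some scores will be missing and others may reflect other treatment. The estimate may also be smaller than in compliers.
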